### **Plans to promote participant retention and complete follow-up {18b}**

Participants will receive reminders to participate by e-mail.

### **Data management {19}**

Anonymized SPSS-files with the collected data will be provided by the research agency. These files will be stored at Amsterdam UMC for 15 years (participants will be informed about this).

### **Confidentiality {27}**

The SPSS files will be anonymized by the research agency. Only the research team will be allowed access to participant's data.

### **Plans for collection, laboratory evaluation and storage of biological specimens for genetic or molecular analysis in this trial/future use {33}**

N/A

## **Statistical methods**

### **Statistical methods for primary and secondary outcomes {20a}**

Statistical analyses will be performed in SPSS for Windows version 26. Linear and logistic regression analyses will be performed to analyse the data.

### **Interim analyses {21b}**

N/A

### **Methods for additional analyses (e.g. subgroup analyses) {20b}**

We will investigate whether the effects on the outcomes measures are modified by gender (i.e., whether the intervention affects men and women differently). If effect modification is the case, we will perform the analyses for men and women separately. Moreover, we will conduct a sensitivity analysis: we will investigate whether the active choice intervention results in better psychological outcomes in participants who prefer an active decision-making role, or shared decision-making, compared to participants who prefer a passive decision-making role.

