## **Objectives {7}**

To test the effect of an online active choice intervention regarding coping with increased risk of cardiovascular disease on psychological outcomes among adults aged 40 to 65 years, and to investigate whether effects differ between men and women.

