## Sample size {14}

The study is powered to detect 0.15 points difference in 'Degree of active choice' in men as well as in women, using an alpha level of .05 and a statistical power of 80%. This means that 206 men and 156 women are required per group. Since we have two groups, a sample size of n=724 is required (i.e., 412 men and 312 women).

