### Statistical analyses

- Before conducting the regression analyses, we will check whether the assumptions have been met:
- Assumptions for linear regression analysis:
  - Dependent variable has a normal distribution
  - Linear relation between independent and dependent variable
  - Also: <https://www.statisticssolutions.com/assumptions-of-linear-regression/>
- Assumptions logistic regression analysis:
  - <https://www.statisticssolutions.com/assumptions-of-logistic-regression/>
- Moreover, we will investigate:
  - Confounding by Age on the 3 primary outcome measures (i.e., degree of active choice, intention strength and commitment). If confounding is found, we will also check whether it applies to the secondary outcome measures, and we will correct for age in the main analyses.
  - Effect modification by gender, educational level (3 levels), health condition (yes/no), and decision making preferences (active/passive) on the 3 primary outcome measures (i.e., degree of active choice, intention strength and commitment). If effect modification is found, we will also check whether it applies to the secondary outcome measures.
- ❖ **Analyses:**
  - **Active Choice**  
Linear regression analysis with condition as independent variable and Degree of Active Choice as dependent variable.
  - **Intention strength**  
Linear regression analyses with condition as independent variable and Intention strength as dependent variable.

- **Commitment**  
Linear regression analysis with condition as independent variable and Degree of commitment as dependent variable.
- **Intention**  
Multinomial logistic regression analysis with condition as independent variable and Intention as dependent variable.
- **Lifestyle Intention: diet**  
Logistic regression analysis with condition as independent variable and intention to change diet as dependent variable.
- **Lifestyle Intention: physical activity**  
Logistic regression analysis with condition as independent variable and intention to change physical activity as dependent variable.
- **Self-efficacy**  
Linear regression analysis with condition as independent variable and Self-efficacy as dependent variable.
- **Response efficacy: lifestyle**  
Linear regression analysis with condition as independent variable and Response efficacy as dependent variable.
- **Response efficacy: medication**  
Linear regression analysis with condition as independent variable and Response efficacy as dependent variable.
- **Autonomous Motivation**  

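### The sample size rests on 80% power within each sex, but the within-sex analyses are run only if an undefined effect-modification criterion is met

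*Protocol*

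**What the plan says.** Protocol, Sample size {14}, states that the study can detect 0.15 points in Degree of active choice "in men as well as in women, using an alpha level of .05 and a statistical power of 80" percent. It continues: "This means that 206 men and 156 women are required per group". Doubling for two groups gives 412 men and 312 women, 724 in all. No calculation for men and women together is given.

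Protocol, Objectives {7}, includes the aim "to investigate whether effects differ between men and women". Section {20b} takes this up ("We will investigate whether the effects on the outcomes measures are modified by gender") and then sets the condition: "If effect modification is the case, we will perform the analyses for men and women separately".

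The SAP, Statistical analyses, plans to examine "Effect modification by gender, educational level (3 levels), health condition (yes/no), and decision making preferences (active/passive) on the 3 primary outcome measures". The only consequence it states is "If effect modification is found, we will also check whether it applies to the secondary outcome measures". Each model it then lists has condition as the independent variable and is fitted in everyone. Age is the one possible addition ("we will correct for age in the main analyses", if confounding is found). Neither document gives a test, a significance level or a threshold for calling effect modification present.

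**The concern.** The sample size is justified by analyses that the protocol makes conditional and the SAP does not list. Power of 80% in each sex holds if the within-sex test is always carried out. If it is carried out only after effect modification has been declared, the chance of running it and finding the effect is lower, sometimes much lower.

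The case that matters is one sex responding more than the other, which is what the gender objective asks about. The plan could then yield a significant pooled effect and no estimate by sex, although enough men and women were recruited to estimate both. Because no criterion is written down, the decision to split could also be taken after the results are seen.

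**Working it through.** **Inputs from the protocol.** Difference 0.15, alpha 0.05, power 80%, 206 men and 156 women per group ({14}); 1:1 allocation ({8}).

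**Assumptions.** The documents give no SD, no sidedness and no criterion for effect modification. I take two-sided sizing and, as the criterion, a two-sided interaction test at 0.05, 0.10 or 0.20. One-sided sizing is shown as a variant.

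**The plan's own figure.** 2 × 206 = 412, 2 × 156 = 312, and 412 + 312 = 724, as stated. The numbers per sex cannot be derived without an SD, so I solved for it with the two-sample t-test:
- men: standardised difference 0.2767, SD = 0.15 / 0.2767 = 0.542
- women: standardised difference 0.3182, SD = 0.15 / 0.3182 = 0.471

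The SD ratio is about √(206/156) = 1.15 under either sidedness.

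**Standard errors.** SE = SD × √(2/n):
- men: 0.542 × √(2/206) = 0.0534
- women: 0.471 × √(2/156), about 0.0533
- difference between the sexes: the root of the sum of squares, 0.0755

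**Power of the interaction test for a 0.15 difference, alpha 0.05.** 0.15 / 0.0755 = 1.987, and Φ(1.987 − 1.960) is about 0.51. This hardly depends on the unseen SDs. Power of 80% in each sex means effect/SE of about 1.960 + 0.842 = 2.802. The SE of the difference is √2 times larger, and 2.802 / 1.414 = 1.98, which again gives about 51%. The difference detectable with 80% power is 2.80 × 0.0755, about 0.21 points.

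**The two-step procedure.** Interaction test first, then the within-sex test only if the first is significant (4,000,000 simulated draws for the second step). Entries are percentages at interaction alpha 0.05 / 0.10 / 0.20. If always run, the within-sex test has about 80% power for 0.15 in every row.

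| True effect, one sex / other | Interaction declared | Sex with +0.15: test run and significant |
|---|---|---|
| 0.15 / 0 | 51.1 / 63.4 / 76.0 | 49.0 / 59.4 / 68.9 |
| 0.15 / 0.075 | 16.8 / 26.2 / 39.8 | 16.6 / 25.5 / 37.8 |
| 0.15 / 0.15 | 5 / 10 / 20 | 2.8 / 6.0 / 13.0 |
| +0.15 / −0.15 | 97.8 / 99.0 / 99.6 | 80.0 / 80.2 / 80.2 |

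When only one sex responds, the pooled test is significant but no analysis by sex follows in 27.8 / 20.4 / 13.0% of trials (men respond) or 21.5 / 16.5 / 11.2% (women respond).

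**Pooled comparison.** Pooled SD = √[(206 × 0.542² + 156 × 0.471²) / 362] = 0.513. With 362 per arm, SE = 0.513 × √(2/362) = 0.0381. Then 0.15 / 0.0381 = 3.94, and power is about 97.6%.

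**One-sided sizing instead.** SDs are 0.611 and 0.532, and the SE of the difference is 0.0852. For 0.15 versus 0, interaction is declared in 42.2 / 54.7 / 68.6% of trials, and the affected sex is shown (one-sided within-sex test) in 40.9 / 52.1 / 63.4%. The difference detectable with 80% power at 0.05 is about 0.24, and pooled power is 93.6%.

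**The case against.** The sample size section describes what 724 participants can detect; it does not promise that a within-sex test will be reported. Splitting only when effects differ is common practice. Under the scenario that {14} describes, 0.15 in both sexes, the main analysis has 97.6% power and the low chance of a within-sex result harms no conclusion. The serious losses need unequal effects that the documents do not posit and a criterion they do not state. The gender check itself is always run, and protocol {20b} supplies the split that the SAP omits. If the check uses a condition-by-gender term, the estimates by sex are already in the fitted model.

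Much of this stands. The pooled result is safe, the condition takes nothing from the gender check, and the size of the loss depends on the assumed alpha: 49% at 0.05 but 69% at 0.20. With opposite effects almost nothing is lost.

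It does not remove the point. Splitting only on interaction is reasonable in a trial sized for a pooled test, but here the analyses made conditional are the ones that set the sample size. At all three alphas, and under either sidedness, the one-sex scenario falls short of 80%. That a criterion has to be assumed is itself part of the defect. Estimates that could be read from an interaction model are not estimates the plan commits to report.

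The SAP leaves the criterion equally open for education, health condition and decision preference. That is a fair addition.

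**Conclusion.** The concern holds and should be fixed. That the sizing analyses are conditional, that no criterion is given and that the SAP lists no analysis by sex follows directly from the text. The written procedure does not deliver 80% power within each sex unless the two effects differ widely.

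The size of the loss is illustrative. It rests on back-solved SDs and an assumed interaction test. When one sex gains 0.15 and the other nothing, the responding sex is shown in roughly half to two-thirds of trials (49% to 69%; 41% to 63% under one-sided sizing) instead of 80%. With 0.15 against 0.075 it is 17% to 38%.

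The pooled comparison is well powered and unaffected. Separately, the always-run gender check has only about 51% power for a 0.15 difference (42% under one-sided sizing), which {14} does not say. A null result there could be misread as no difference.

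**What to change.** Keep the pooled comparison as the main analysis. In {20b} and the SAP, replace the conditional split with text such as:

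> For each of the three primary outcomes we will always report the effect in men, the effect in women and their difference, each with a 95% CI. Estimates come from separate linear regressions by gender (or one model with robust standard errors), with the same age adjustment as the main model. They are secondary to the pooled test and not adjusted for multiplicity. Gender is declared an effect modifier if the two-sided 95% CI of the difference excludes 0 on at least one primary outcome. The check is then extended to the secondary outcomes, and any that meets the same criterion is also analysed by gender.

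If another alpha is preferred, fix it before the data file is received. Separate fits or robust standard errors are advised because {14} implies unequal SDs (ratio about 1.15). State a criterion for the SAP's other three modifiers as well.

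In {14}, add:

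> The 80% refers to the within-sex analyses of Degree of active choice, which are always run. Power for a 0.15-point difference between the sexes is about 51% at two-sided 0.05 (80% at about 0.21 points). A non-significant interaction will not be read as absence of a gender difference.

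If sizing was one-sided, the figures become about 42% and 0.24 points. Keep only the version that matches the actual sizing.

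A check of the proposed analysis (separate age-adjusted fits, 100,000 simulated trials) gave power of 80.0% in men and 79.8% in women, type I error of 5.0% and 5.1%, and 95.0% coverage for the CI of the difference.

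The cost is wording and nine further estimates (three for each of three outcomes), with no extra participants. The intervals are unadjusted, and the trigger for the secondary outcomes opens falsely about 8% to 14% of the time at 0.05 (correlation between outcomes 0.9 down to 0). The stated power for the gender question also becomes less favourable.

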### **Methods in analysis to handle protocol non-adherence and any statistical methods to handle missing data {20c}**

Pairwise deletion will be used for missing data.

### **Plans to give access to the full protocol, participant level-data and statistical code {31c}**

Data will be available upon reasonable request.

## **Oversight and monitoring**

### **Composition of the coordinating centre and trial steering committee {5d}**

Research team CHOICE of the AmsterdamUMC, Department of Public and Occupational Health, will

coordinate and steer the trial. This team consists of five researchers who meet bimonthly.

### **Composition of the data monitoring committee, its role and reporting structure {21a}**

An independent research agency will collect and monitor the data. After collecting the data, the research agency will send the data to the CHOICE research team (Amsterdam UMC).

### **Adverse event reporting and harms {22}**

N/A

### **Frequency and plans for auditing trial conduct {23}**

N/A

### **Plans for communicating important protocol amendments to relevant parties (e.g. trial participants, ethical committees) {25}**

Important protocol modifications will be communicated to the ethical committee of Amsterdam UMC.

### **Dissemination plans {31a}**

Publication in a scientific journal.

### **Discussion**

If an active choice process regarding coping with an increased CVD risk indeed results in better outcomes compared to an advice, the active choice intervention could be implemented by GP's. GP's could either use it as a tool during their consultation, or send it to their patients, so the patients can read the information and clarify their own values before making a choice. Providing patients with a choice – instead of giving advice – respects their autonomy. Ultimately, it is expected that an active choice process will increase patients' adherence to the chosen option; e.g., a healthier lifestyle or medication use.

### **Trial status**

Protocol version 1, 19-11-2021. Start recruitment: January 2022. End recruitment: January 2022.

### **Abbreviations**

N/A Not applicable; CVD Cardiovascular disease.

## **Declarations**

### **Acknowledgements**

*Not applicable*

### **Authors' contributions {31b}**

*Not applicable*

### **Funding {4}**

No external funding was received for this study.

### **Availability of data and materials {29}**

Data will be available upon reasonable request.

### **Ethics approval and consent to participate {24}**

Ethical review is currently being performed at Amsterdam UMC. Reference: 2021.0676. Only participants who provide informed consent will be included in the study.

### **Consent for publication {32}**

Not applicable.

### **Competing interests {28}**

The authors declare that they have no competing interests.

### RESEARCH QUESTION

What is the differential impact on psychological outcomes between promoting an active and a passive choice process regarding lifestyle changes and medication use to reduce cardiovascular risk?

### HYPOTHESIS

Promoting an active choice regarding lifestyle changes and medication use to reduce cardiovascular risk has a different impact on psychological outcomes compared to promoting a passive choice.

### DESIGN

Online randomized controlled trial with two conditions: active choice condition (intervention) versus passive choice condition (control).

### STEPS IN DATA PREPARATION, CLEANING, CODING AND ANALYSIS

#### Preparation, cleaning, editing, coding

- Rename variables; this will make interpretation of the variables easier. We will do this using syntax.
- Selection of participants that meet the inclusion criteria.
- Recode variables that need to be recoded.
  - o If participants intend to change their lifestyle and take medication, they will be asked more questions (i.e. for lifestyle and medication separately). For these participants, we will use the highest score on the items (and not the average).
  - o For the 4 knowledge items, we will merge the 'wrong answer' with the option 'Don't know'.
  - o We will dichotomize the control preferences scale (5-point scale) for the analysis of effect modification. As a research team, we decided that we will consider scores 1-2 as 'active preference' and scores 4 and 5 as 'passive' preference. Score 3 (preference for shared decision making) will not be used in the analysis.

- Check frequencies and descriptives to check for missing data and distributions.  
*Missing data will be indicated as 'system missing' by the research agency. We will exclude missing values pairwise in the analyses.*
- Construct scales/composite scores: we will create composite scores for items that belong together and that show reasonable internal consistency (i.e., a Cronbachs alpha of .70 or higher). Composite scores will be calculated by adding up the score on the items and dividing them by the number of items.
  - ❖ The Treatment Self-regulation Questionnaire website ([Treatment Self-Regulation Questionnaire – selfdeterminationtheory.org](http://Treatment-Self-Regulation-Questionnaire-selfdeterminationtheory.org)) says: “Each participant gets a score on each subscale by averaging responses to each of the items that make up that subscale.” Since we only include the ‘Autonomous Motivation’ subscale, we will average the items of this subscale.

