## Outcomes {12}

All outcomes will be assessed directly after the intervention. Overview of outcome measures:

Outcome	Number of items	Scale
Intention regarding coping with CVD	1	Nominal; 4 options: Lifestyle change/ Medication use/ Lifestyle change and medication use/ Change nothing
Intention strength	1	Scale of 1 (not strong at all) to 10 (very strong)
Degree of active choice	11	A 5-point scale will be used for the items (1: totally disagree; to 5: totally agree). The average of all 11 items will be used as composite score.
Values congruence	1	A 10-point scale will be used: 1 (not at all) to 10 (totally).
Commitment	3	A 10-point scale will be used: 1 (not at all) to 10 (totally).
Self-efficacy	1	A 10-point scale will be used: 1 (not at all) to 10 (totally).
Response efficacy	2	A 10-point scale will be used: 1 (not at all) to 10 (totally).
Autonomous motivation & controlled motivation	12	The Treatment Motivation Questionnaire will be used. This questionnaire contains 2 subscales: Autonomous motivation and Controlled motivation. Items are on a scale of 1 (not at all true) to 7 (very true).
Knowledge – illness representations	4	4 items on a scale of 1 (totally disagree) to 5 (totally agree).
Risk perception: Cognitive and affective risk appraisal	3	1 item assesses cognitive risk appraisal (on a scale ranging from 'very small risk' to 'very high risk'. 2 items assess affective risk appraisal on a scale of 1 (not at all) to 10 (totally)
Lifestyle intention	1	Nominal; 4 options: Quit smoking; Healthier diet; More physical activity; Other.
Lifestyle intention strength	1	Scale of 1 (not strong at all) to 10 (very strong)
Perceived health	1	Item from RAND-36. Scale: 1 (very bad) to 5 (very good).
Preferred decision-making role	1	Item based the Control Preferences Scale of Degner et al. (1992). Contains 5 options to assess preference for a more passive or more active role in decision-making about treatment.

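### The SAP words the 'highest score' rule at item level, ahead of composite construction, so on any multi-item scale asked twice a participant who chooses both options can score above both of their real scale scores

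*SAP*

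**What the plan says.** The SAP section on preparation, cleaning, editing and coding lists its steps in order. Under the recoding of variables it states: "If participants intend to change their lifestyle and take medication, they will be asked more questions (i.e. for lifestyle and medication separately". The next sentence gives the combination rule: "For these participants, we will use the highest score on the items (and not the average".

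Scale construction comes in a later bullet. A composite is formed only under a consistency condition: "we will create composite scores for items that belong together and that show reasonable internal consistency (i.e., a Cronbachs alpha of .70 or higher". The scoring rule is: "Composite scores will be calculated by adding up the score on the items and dividing them by the number of items". For Autonomous motivation the SAP cites the instrument's scoring instruction, "Each participant gets a score on each subscale by averaging responses to each of the items that make up that subscale", and adds that "we will average the items of this subscale".

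The Protocol's Outcomes table gives Commitment 3 items on a 1-10 scale. The SAP's statistical analyses section names Commitment as one of three primary outcomes, with degree of active choice (11 items) and intention strength (1 item). Neither document says which items are asked twice, and no sentence describes taking the highest at scale level.

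**The concern.** The rule speaks of items and stands before the step that averages items. Someone coding the steps in sequence would replace each twice-asked item by the larger of its two answers and then average the replaced items. On a multi-item scale, the first item may then come from the lifestyle answers and the second from the medication answers. The composite describes neither behaviour.

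Three things are at stake.

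- **Comparability.** Participants who chose a single option keep a true scale score, while those who chose both may receive one that they gave for neither behaviour. The error only goes upward.
- **The arm comparison.** Choosing both happens after randomisation, and the arms receive different messages about it. The Protocol abstract has controls reading advice to do both, while the intervention group weighs four options. If the shares differ, the excess does not cancel.
- **The consistency check.** For these participants, Cronbach's alpha would be computed on items that mix two behaviours, and alpha decides whether the composite is formed.

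**Working it through.** The documents give no figure for this rule, so there is none to reproduce.

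**Mechanism.** Let a participant give answers L1..Lk for lifestyle and M1..Mk for medication. Each max(Li, Mi) is at least Li and at least Mi, so mean of max(Li, Mi) ≥ max(mean L, mean M). The inequality is strict exactly when lifestyle is higher on at least one item and medication on at least one other.

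- L = 9, 5, 7 (mean 7) and M = 6, 8, 7 (mean 7) recode to 9, 8, 7, mean 8. This is above both real scores.
- L = 9, 8, 8 (mean 8.33) and M = 7, 6, 7 (mean 6.67) recode to 9, 8, 8, mean 8.33. This equals the lifestyle score, so nothing is distorted.
- With one item, the maximum is one of the two real answers, so no mixing can occur.

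**Average excess on a 3-item scale.** From the Protocol: 3 items, scale 1-10. Assumed: item SD 2, normal answers, equal means for the two behaviours, item correlation w within a behaviour and c across behaviours. For two such variables, the expected maximum exceeds their average by SD(difference) × 0.3989, where 0.3989 = 1/√(2π).

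- Item-level rule: A = 0.3989 × 2√(2(1 − c))
- Higher of two composites: B = 0.3989 × 2√(2[(1 + 2w)/3 − c])
- Artefact of mixing items: A − B

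| w | c | A | B | A − B | (A − B)/A |
|---|---|---|---|---|---|
| 0.7 | 0.4 | 0.874 | 0.714 | 0.16 | 18% |
| 0.5 | 0.3 | 0.944 | 0.683 | 0.26 | 28% |
| 0.6 | 0.5 | 0.798 | 0.545 | 0.25 | 32% |

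Simulation of the same model agrees, and puts 50%-65% of 'both' choosers above both real scale means.

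**More realistic answers.** All results below are from simulation, and the excess is averaged over all 'both' choosers.

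- Answers rounded and truncated to 1-10 around an assumed mean of 7: excess about 0.15-0.25, share above both real means 32%-46%.
- In addition, medication rated 1 point lower and the correlation between the two askings of the same item raised by 0.2: share about 13%-32%, excess down to about 0.05 at the low end.
- A wider grid, with item correlation up to 0.9 and mean gaps up to 2 points: share 2%-54%, excess 0.01-0.31.

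**Autonomous motivation.** The number of items is not stated; 6 of the 12 are assumed, with item SD 1.4. The first model gives an excess of about 0.14-0.24 points.

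**Effect on the arm difference.** If the excess is the same in both arms, the shift is excess × difference in 'both' shares. With an assumed gap of 20 percentage points:

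- 0.16 × 0.20 = 0.032
- 0.26 × 0.20 = 0.052
- at the low end, 0.05 × 0.20 = 0.01

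For scale, the composite SD is 2√((1 + 2w)/3) = 1.63-1.79. With 206 + 156 = 362 per arm, the standard error is SD × √(2/362) = 0.12-0.13, and the difference detectable with 80% power is about 2.80 × SE = 0.34-0.37. The artefact is therefore at most 0.052/0.121 = 0.43 of a standard error.

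**The case against.** The strongest reply is that the effect is small and the order is inferred. Much of this stands.

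- **Order of steps.** A reader might infer that the SAP definitely takes the maximum before averaging. It does not say so outright, and a scale-level maximum remains possible. The wording and the sequence of bullets make it the less natural reading, and no sentence supports it. If it was intended, the text still needs changing.
- **Scales affected.** A reader might take it as settled that Commitment is scored this way. Neither document lists the twice-asked items. Response efficacy is analysed separately for lifestyle and medication, so no maximum is evident there, and nothing shows that the 11 active-choice items are asked twice.
- **Frequency.** A reader might infer that most 'both' choosers are affected. The documents contain no figure for this. The 50%-65% comes from the least favourable of the models in the text and falls considerably with bounded answers, a preferred behaviour, or similar answers to the same question.
- **Consequence.** A reader might infer that the trial's conclusion is at risk. The documents give no 'both' shares by arm, and even a 20-point gap yields a shift of less than half a standard error.
- **Instrument rule.** It is tempting to say that the SAP breaks the scoring instruction it cites. That sentence does not address a questionnaire given for two behaviours, and the SAP still averages items. At most, a mixed composite fits it poorly.
- **Larger inflation.** Taking the higher of two real composites still lifts the score by about 0.55-0.71 points over the person's own average, against 0.16-0.26 from mixing items. That is correct, and reordering does not address it.

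None of this removes the defect: as worded and ordered, the rule can produce a score that the participant gave for neither behaviour.

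**Conclusion.** The point holds in a limited form. Followed as written, the item-level maximum can give 'both' choosers a composite above both of their real scale scores, and never one below the higher. That direction is algebra and needs no assumption.

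The size does depend on assumptions about correlations, means and item SD. A reasonable working range for a 3-item 1-10 scale is 0.05-0.26 points averaged over 'both' choosers, with about 13%-65% of them above both real means; more extreme assumptions fall outside it. The effect on the arm difference is about 0.03-0.05 points for an excess of 0.16-0.26 at an assumed 20-point gap in shares, and less if the excess or the gap is smaller. It is unlikely to change a conclusion by itself.

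The change is still worth making. The rule plausibly reaches a primary outcome, leaves a coding choice open, and costs almost nothing to settle before the data are analysed.

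**What to change.** In the SAP's recode and composite steps:

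1. List the items that are asked separately for lifestyle and medication.
2. For multi-item scales, state: *For multi-item scales, compute the lifestyle and medication composites separately, then use the higher of the two composites.* Apply this to every twice-asked multi-item scale, including Commitment and Autonomous motivation if they are among them.
3. Compute Cronbach's alpha on the unmixed item sets.
4. Keep the item-level rule for single-item outcomes.

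The cost is a short list, a sentence or two in the SAP and a reordering of the SPSS syntax; no new data are needed. The change keeps the sponsor's preference for the highest over the average, and with it the upward shift which that preference brings.

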## Participant timeline {13}

After clicking the link to the study and providing informed consent, participants will be randomized to the intervention or control group. Directly after the intervention, participants are asked to complete the questionnaire.

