## **Data collection and management**

### **Plans for assessment and collection of outcomes {18a}**

The questionnaire items are listed in the table of outcomes.

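### The SAP drops participants who prefer shared decision-making from the decision-preference analysis, contrary to the protocol and without a reason; the preference is also measured after the intervention.

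*SAP*

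**What the plan says.** **Grouping.** Protocol section {20b} asks whether the intervention does better in "participants who prefer an active decision-making role, or shared decision-making, compared to participants who prefer a passive decision-making role". The SAP's data-preparation section codes scores 1-2 of the control preferences scale as active and 4-5 as passive, then adds: "Score 3 (preference for shared decision making) will not be used in the analysis". It presents the coding as a decision of the research team and does not mention the protocol's grouping.

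**Use.** The SAP's statistical analyses section tests effect modification by "decision making preferences (active/passive) on the 3 primary outcome measures", alongside gender, educational level and health condition. It continues: "If effect modification is found, we will also check whether it applies to the secondary outcome measures".

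**Timing.** Protocol section {13} places randomisation after consent, and then: "Directly after the intervention, participants are asked to complete the questionnaire". Section {18a} says of that questionnaire: "The questionnaire items are listed in the table of outcomes". The table in section {12} includes the preferred-role item ("Contains 5 options to assess preference for a more passive or more active role in decision-making about treatment") under the statement "All outcomes will be assessed directly after the intervention". Neither document describes asking the item at baseline.

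**The concern.** There are two separate points.

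1. **The documents define different contrasts.** The protocol's sentence can mean one combined active-or-shared group, or two groups each compared with passive. Either way the shared group is in, and the SAP takes it out. Active versus passive is a legitimate question, but a narrower one, and readers are not told why it replaced the protocol's.

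2. **The modifier is measured after randomisation.** The intervention arm has just weighed pros and cons and completed a value-clarification exercise; section {6b} says the control arm is not prompted in this way. If that changes how people answer the preference item, the subgroups no longer contain comparable people in the two arms. A condition-by-preference interaction can then appear although the true effect does not depend on preference, and the SAP would carry it into a check on the secondary outcomes. Leaving out score 3 also becomes a selection on a post-randomisation answer.

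The grouping mismatch does not cause the timing problem, and returning to the protocol's grouping does not cure it.

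**Working it through.** **Inputs from the documents.** Protocol section {14}: difference 0.15 in Degree of active choice, alpha .05, power 80%, 206 men and 156 women per group. The total reproduces: 2 × (206 + 156) = 724.

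**SD (not given).** Solving the two-sided two-sample t-test for 0.15 at 80% power gives 0.542 for men and 0.471 for women. Pooled: √[(206 × 0.542² + 156 × 0.471²)/362] = 0.513.

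**Assumptions.** The documents give no distribution for the preference item. I take 20, 40 or 60% shared and 10 or 20% passive.

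**Point 1: cost of dropping score 3.** Numbers left out: 0.20 × 724 = 145; 0.40 × 724 = 290; 0.60 × 724 = 434.

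Interaction SE = SD × √(4/n₁ + 4/n₂), where n₂ is the passive group and n₁ is the active group (SAP) or active plus shared (protocol). Power is for a true interaction of 0.15.

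| Passive | Shared | n active / passive | SE, SAP | SE, protocol | Ratio | Power, SAP | Power, protocol |
|---|---|---|---|---|---|---|---|
| 10% | 20% | 507 / 72 | 0.129 | 0.127 | 1.01 | 21% | 22% |
| 10% | 40% | 362 / 72 | 0.132 | 0.127 | 1.04 | 21% | 22% |
| 10% | 60% | 217 / 72 | 0.139 | 0.127 | 1.10 | 19% | 22% |
| 20% | 20% | 434 / 145 | 0.098 | 0.095 | 1.03 | 33% | 35% |
| 20% | 40% | 290 / 145 | 0.104 | 0.095 | 1.10 | 30% | 35% |
| 20% | 60% | 145 / 145 | 0.121 | 0.095 | 1.26 | 24% | 35% |

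The ratios do not depend on the SD.

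**Point 2: false interaction if answers shift by arm.** I simulated a latent normal preference cut into passive, shared and active with the shares above. Its correlation with the outcome was 0, 0.3 or 0.5, the mean effect was 0.15 whatever the baseline preference, and each scenario used 2,000,000 draws (Monte Carlo error about 0.003-0.005). The shift is the rise in active answers in the intervention arm, in percentage points. False-positive rate = P(|N(bias/SE, 1)| > 1.96).

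| Model | Shift | Bias, SAP | Bias, protocol | False positives |
|---|---|---|---|---|
| No shift | 0 | 0.00 | 0.00 | 5% |
| Everyone shifts, effect 0.15 for all | 5-10 | up to 0.03 | up to 0.05 | 5-7% |
| Half respond (effect 0.30, others 0) and only they shift | 5-10 | 0.04-0.12 | 0.03-0.11 | 6-16% |
| As above, extreme case | 15 | up to 0.16 | up to 0.12 | 24-29% at the worst SAP setting |

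The bias is at most 0.4 SE in the second row and about one SE in the third. In the last row the worst SAP setting is 1.26 SE using the shifted group sizes, or 1.40 SE using the baseline shares; hence 24% and 29%. The 15-point shift is infeasible at 10% passive with 20% shared and was left out.

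**The case against.** - **The SAP states its rule openly and in advance, and power is poor under either grouping.** True. The fault is an unexplained inconsistency, not concealment, and what is lost is mainly information on the shared group rather than precision.
- **The protocol already sets this analysis apart, calling it a sensitivity analysis among its additional analyses.** It does. That wording gives no warning that the modifier is measured after randomisation, and the SAP does not repeat it.
- **The item's position is inferred.** No sentence states it directly, and the item is listed as an outcome but used only as a modifier. Even so, sections {12}, {13} and {18a} all point the same way.
- **The larger bias figures need responders, and only responders, to shift.** Nothing in the documents supports that. They do not say the intervention aims to change this preference, and with an equal shift the false-positive rate is nearly nominal. The figures show what could happen, not what is expected.
- **Other modifiers may share the problem.** The SAP does not give the source or timing of health condition. If it comes from the perceived-health item in the same table, it has the same weakness. This is open and does not weaken the point about preference.
- **The assumed passive share is arbitrary.** Yes. At 30% passive the SE inflation would be 6-67%, which enlarges the loss.

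**Conclusion.** The concern holds and is minor. The mismatch between the protocol and the SAP is clear from the text, and post-intervention measurement is the natural reading of the protocol. I hold both with high confidence.

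The sizes are less certain. The loss under point 1 depends on the assumed preference shares. Any bias under point 2 depends on a shift between arms that may not occur. All figures are for Degree of active choice; intention strength and commitment, the other two primary outcomes in the SAP, have no SD from which to calculate.

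Reach is limited: this is one of four effect modifiers, and the recode removes nobody from the main comparisons between conditions, missing values aside.

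**What to change.** **Grouping.** Replace the two-group rule with a condition-by-preference interaction at three levels (active, shared, passive), fitted in all participants. This keeps the SAP's active-versus-passive contrast and restores the protocol's shared group. Combining active and shared against passive would also match one reading of the protocol. If score 3 is still to be omitted, the SAP should say why, though that leaves the protocol's question unanswered.

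**Timing.** If the item stays after the intervention, or has already been asked there, report its distribution by arm first. Label this analysis, and any secondary-outcome check that follows from it, exploratory. The label does not remove bias, but with the table readers can judge how likely it is.

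**Cost.** One or two SAP sentences and one table, with no change to trial conduct.

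**Alternative.** Asking the single item after consent and before randomisation would remove the timing problem. It means moving one web item and carries a small risk of priming, possibly greater in the control arm, which is meant not to reflect on its preferences. That could narrow the main contrast for the sake of a minor analysis, so it is not the lead option.
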